8.5 Statistical Analysis

This study will employ a descriptive approach to analyse the collected data. Prior to finalising the statistical approach, the distribution of key variables will be assessed. In cases where variables show significant skewness, data transformation techniques, such as logarithmic transformation, will be considered to improve normality.

Patient records discussed by the MDT panels will be reviewed and analysed. For the complex case MDTs (RNOH Anaesthetics MDT and Royal Free Colorectal Cancer MDT), all cases discussed during the study pre-intervention, intervention and post-intervention phases will be included in the study analysis.

For the high-volume MDTs (Royal Free Breast Cancer MD), approximately 25% cases are expected to be submitted using Salutare One Referral during the intervention period. A formal comparison of the pre-intervention and intervention study cohort will be made. At the end of the study, raw data will be processed for summary and descriptive statistics. The distribution of times from referral to MDT decision & implementation will be assessed to check if mean or median most appropriate to use.

Normally distributed data will be reported as means with 95% confidence intervals (CIs), while non-normally distributed data will be presented as medians with interquartile ranges (IQRs). Categorical variables will be summarized using proportions or percentages, accompanied by their corresponding 95% CIs.

Pending normality testing using the Kolmogorov-Smirnov Test, a combination of Multivariate Mixed-Effects Models and Generalized Linear Mixed Models (GLMMs), the latter for categorical, ordinal, and binary measures, will be carried out for comparing the system usability scales the acceptance of the null hypothesis.

Title: Salutare Dialogue for MDTs					
Authors	[name], [name], [name]	Ver.2		Date Authorised	22/01/2025

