11.3 Intervention Assessment

An intervention assessment will be administered to collect participant views regarding the current safety, efficiency and effectiveness of the MDT.

Title: Salutare Dialogue for MDTs					
Authors	[name], [name], [name]	Ver.2		Date Authorised	22/01/2025

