16.6 Confidentiality

All information collected about study participants in relation to this study will be kept strictly confidential. All participants will be assigned a non-identifiable study number and the data collected in the study will be linked to this number. The study participation itself cannot be kept confidential as the study participants might need to engage with the Salutare study research team. Their participation will also be known to other study participants as they will interact daily as part of the MDT panels.

MDT meetings will be observed (either directly or via reviewing MDT meeting transcripts) by NHS researchers to collect data on the MDT review duration, quality and outcomes. This data will be pseudonymized by NHS researchers.

The patient information processed by the One Referral system includes information required to complete an MDT referral. This includes five key sections for each referral, plus any additional information the referrer wishes to provide. It should be noted that images and histology are not accessed through the platform, but the system is a means to allow transfer requests.

Title: Salutare Dialogue for MDTs					
Authors	[name], [name], [name]	Ver.2		Date Authorised	22/01/2025

1. Brief medical history
2. Details of prior MDT discussions, treatments, or relevant history
3. The question or questions being asked to the MDT
4. Whether the patient is aware of the referral to the MDT
5. An assessment of frailty or fitness of the patient

This data will be processed for the purpose of direct care provision.

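### Section 8.5 words its mixed models only for the usability scales, so the linked staff questionnaires repeated at baseline and intervention get no within-person comparison

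*Protocol*

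**What the plan says.** Section 8.5 opens with "This study will employ a descriptive approach to analyse the collected data". For continuous data, "Normally distributed data will be reported as means with 95% confidence intervals (CIs"), and medians with interquartile ranges where the data are not normal. "Categorical variables will be summarized using proportions or percentages, accompanied by their corresponding 95% CIs". The closing paragraph then names "a combination of Multivariate Mixed-Effects Models and Generalized Linear Mixed Models (GLMMs), the latter for categorical, ordinal, and binary measures", which "will be carried out for comparing the system usability scales the acceptance of the null hypothesis". Words seem to be missing from that sentence, but the only outcome it names is the usability scale. It states no random effect.

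The surveys are described elsewhere:

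- Section 11.1: the baseline survey (Day 0) asks for views on the MDT's current safety, efficiency and effectiveness.
- Section 11.2: the onboarding survey includes the SUS. It is the only assessment for which the SUS is named.
- Section 11.3: "An intervention assessment will be administered to collect participant views regarding the current safety, efficiency and effectiveness of the MDT".
- Section 11.4: the post-study survey asks about gains or losses from stopping the software.
- Section 16.6: "All participants will be assigned a non-identifiable study number and the data collected in the study will be linked to this number".

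Section 7.3 sets the secondary objectives as contrasts with and without the software. Section 8.2 lists the participant questionnaire as the only source for MDT performance rating (endpoint 5). Section 8.1 makes user questionnaires part of the primary endpoint.

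**The concern.** The objective is a contrast between conditions, and the same people are asked about the MDT in both. Their answers can be matched by study number. The natural estimate is therefore the change within each person.

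Section 8.5 does name a model class that can use repeated answers, but its wording attaches it to the SUS. The SUS cannot have a value before the software exists, and the assessment sections give it one administration. The questionnaires that are repeated are left with means, medians or proportions.

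Two things are at stake if this is followed as written:

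- **Precision.** A before-and-after change read from two marginal summaries carries between-person variation that pairing would remove. With about 20 staff per MDT this matters.
- **Composition.** Marginal summaries move when the set of respondents changes. Section 15 withdraws staff who leave employment, and some non-response is foreseeable.

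**Working it through.** The protocol gives no SD, within-person correlation, effect size or power for the questionnaires, so it has no figure to reproduce. What follows is an illustration in SD units.

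**Inputs**

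- n = 20 staff for RNOH Anaesthetics, with the same figure for Royal Free Colorectal; n = 50 for Royal Free Breast, on hold (section 1, Target).
- Equal SD at both surveys (assumed).
- Within-person correlation r = 0.3, 0.5 or 0.7 (assumed range).
- All staff answer both surveys (assumed, and relaxed below).

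**95% half-width of the change between two surveys**

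Pairing ignored: t(0.975; 2n − 2) × √(2/n). For n = 20: 2.024 × √(2/20) = 0.640 SD.

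Paired: t(0.975; n − 1) × √(2(1 − r)/n). For n = 20:

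- r = 0.3: 2.093 × √(1.4/20) = 0.554 SD
- r = 0.5: 2.093 × √(1.0/20) = 0.468 SD
- r = 0.7: 2.093 × √(0.6/20) = 0.363 SD

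| n | Pairing ignored | r = 0.3 | r = 0.5 | r = 0.7 |
|---|---|---|---|---|
| 20 | 0.640 | 0.554 | 0.468 | 0.363 |
| 50 | 0.397 | 0.336 | 0.284 | 0.220 |

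Ignoring the pairing widens the interval by a factor of 1.16 to 1.77 at n = 20. In terms of variance, pairing is worth 1/(1 − r) times as many staff: 1.43, 2.0 and 3.33.

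**Does the model class already named deliver this?** In one simulated balanced data set (n = 20, r = 0.5), a random-intercept model gave a standard error of 0.185 for the phase difference. The paired analysis also gave 0.185, and the unpaired one gave 0.254. So the models in section 8.5 keep the pairing, provided they carry a participant random effect and are applied to these items.

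**Incomplete overlap.** Suppose 17 staff answer each survey, 14 answer both, and r = 0.3. Pairing ignored: t(32) = 2.037, × √(2/17) = 0.70 SD. Paired on the 14 only: t(13) = 2.160, × √(1.4/14) = 0.68 SD. The gain almost vanishes in that case.

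**Changing respondents.** If a share f of staff drops out and differs from those who stay by d SD, the later mean shifts by f × d with no real change. For f = 0.1 to 0.3 and d = 0.5 to 1 (assumed), this is 0.1 × 0.5 = 0.05 SD up to 0.3 × 1 = 0.30 SD.

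**The case against.** A reader might infer that section 8.5 summarises each phase separately, throws the pairing away, or treats the two surveys as independent samples. The text does not say so. The sentence on means names neither phases nor questionnaires. Phase-wise aggregates appear in section 12, for some metrics only, and the examples there are case metrics. A mean with a CI assumes nothing about independence between surveys, and no unpaired test is specified. Nor is a comparison of different respondents planned anywhere; that is a risk from leavers or non-response.

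The mixed-model sentence is also plainly damaged. Naming a model class for categorical, ordinal and binary measures suggests a wider scope than the SUS score, and section 8.3 recommends following the same users over time. The authors may well have meant the models to cover all the questionnaires. Random effects and within-person contrasts are also commonly left to a SAP, which may exist.

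Further, the questionnaires are not shown, so identical items at baseline and intervention are inferred from similar descriptions. The two surveys are 14 weeks apart in the complex-case MDTs (Day 0 and Day 98). Section 8.3 calls the SUS the only validated tool, so the correlation for the other items could be low.

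Most of this stands, and it limits the point. It does not remove it. Section 8.5 is not silent: it assigns a method, and as worded it assigns it to the instrument for which only one administration is named. If a wider scope was meant, the sentence still needs correction. The announced formal comparison of the pre-intervention and intervention cohorts does not fill the gap, because it sits in the paragraph on the breast MDT, whose testing is on hold, and gives no method.

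**Conclusion.** The point holds in a limited form. For staff questionnaires repeated at baseline and intervention, section 8.5 states only marginal summaries and no within-person contrast, although the objective is a with-and-without comparison and the answers are linked. It would go too far to say that the plan discards the pairing or compares different people.

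For 20 staff with complete overlap, the cost in precision is a half-width of 0.64 SD instead of 0.55 to 0.36 SD, equivalent to 1.4 to 3.3 times as many staff. This rests on assumed correlations of 0.3 to 0.7 and shrinks when overlap is incomplete.

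The weight is modest. The study is a descriptive pilot, section 8.6 says it is not powered for the secondary outcomes, and no decision rule depends on these intervals. The correction is still worth making, because questionnaires are part of the primary endpoint and section 8.1 intends that endpoint to inform the expansion of the study.

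**What to change.** Repair the mixed-model sentence in section 8.5 so that it states its scope. The (generalised) mixed model, with a participant random intercept and study phase as a fixed effect, should cover the SUS where it is repeated and every questionnaire item asked in the same form in more than one phase. For each such item, report the within-person change with its 95% CI and the number of staff who answered both surveys. Keep the phase-wise means, medians and proportions as description.

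A mixed model also uses staff who answered only one survey, so it loses less than an analysis restricted to complete pairs.

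The cost is one reworded sentence. It needs no new data and no model class beyond those section 8.5 already names.

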Target	
RNOH Anaesthetic MDT: Approximately 20 staff taking part in MDT meeting taking part in the MDT meeting preparation and discussion. We aim to collect data for approximately 40 cases discussed without the Salutare One Referral software and approximately 40 patients discussed with Salutare One Referral.
 
Royal Free (Colorectal Cancer): Approximately 20 staff taking part in MDT meeting taking part in the MDT meeting preparation and discussion. We aim to collect data for approximately 120 cases discussed without the Salutare One Referral software and approximately 120 cases discussed with Salutare One Referral.
 
Royal Free (Breast Cancer): Approximately 50 staff taking part in the MDT meeting preparation and discussion. We aim to collect data for approximately 150 cases discussed without the Salutare One Referral software and 150 patients discussed with Salutare One Referral. (Note: The Royal Free Breast Cancer MDT testing is currently on hold, subject further discussions).
	
Inclusion criteria (Active Study Group)	MDT meeting Panel Members, Coordinators and staff submitting MDT referrals will take part in this study.	
Exclusion criteria (Main study)	MDT meeting Panel Members, Coordinators and staff submitting MDT referrals who are unwilling or unable to take part in the study.	
Duration of study	
The study consists of 4 phases:
 
 1. Pre-intervention period (before-study control) with no access to the Salutare One Referral software. 2. Onboarding period to allow for software installation and staff training and adjustment to the technology 3. Salutare One Referral intervention period 4. Post-intervention period (after-study control) with no access to the Salutare One Referral software 
The total duration of the study will depend on the frequency of MDT meetings and the number of cases discussed.
	

	
 • Stanmore Anaesthetics MDT and Royal Free Colorectal Cancer MDT: The study duration will be approximately 18 weeks (4-week pre-intervention period, 2-week onboarding period, 8-week intervention period, 4-week post-intervention period) • Royal Free Breast Cancer MDT: The study duration will be approximately 10 weeks (2-week pre-intervention period, 2-week onboarding period, 4-week intervention period, and a 2-week post-intervention period). 
Additionally, 4 weeks are allowed to complete the study data collection.

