8.6 Expected Outcomes

The implementation of the Salutare One Referral Software is anticipated to enhance operational efficiencies by improving the quality of pre-assessment information and reducing the time spent preparing for meetings. These enhancements are expected to result in a higher percentage of patients receiving definitive MDT decisions, thereby shortening the patient pathway, including the pre-operative phase for surgical cases. Primary outcomes of the study will evaluate the increased confidence and satisfaction among MDT members in making complex clinical decisions. While this pilot study is not powered to comprehensively evaluate secondary outcomes, future study extension will be conducted to systematically assess the software's effectiveness in supporting MDT meetings and its impact on both patient outcomes and the experiences of MDT members.

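### Protocol section 8.5 gives accepting a null hypothesis as the aim of the usability-score models, which a non-significant result cannot support and which conflicts with the section's descriptive approach

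*Protocol*

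**What the plan says.** Section 8.5 opens with a plain statement of intent: "This study will employ a descriptive approach to analyse the collected data". It plans means with 95% confidence intervals for normally distributed data, medians with interquartile ranges otherwise, and proportions with 95% intervals for categorical data. Its last sentence then says that, subject to a normality test, multivariate mixed-effects models and generalised linear mixed models "will be carried out for comparing the system usability scales the acceptance of the null hypothesis".

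SUS is part of the primary endpoint (section 8.1), and section 8.3 describes it as the study's only validated tool. Section 8.3 also recommends observing users repeatedly and expects scores to improve with experience. In section 11, only the onboarding assessment (11.2) names SUS. The intervention and post-study assessments (11.3 and 11.4) do not.

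The summary in section 1 gives the staff numbers: "RNOH Anaesthetic MDT: Approximately 20 staff taking part in MDT meeting", "Royal Free (Colorectal Cancer): Approximately 20 staff taking part in MDT meeting" and "Royal Free (Breast Cancer): Approximately 50 staff taking part in the MDT meeting preparation and discussion". The breast cancer MDT is on hold.

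**The concern.** A test that fails to reject a null shows only that the data are compatible with no difference. They may be equally compatible with a difference that matters. Concluding that there is no difference needs a margin set in advance and an interval lying inside it. The protocol states no margin for SUS, yet it names acceptance of a null as what the models are for. An analyst following that sentence could report usability as unchanged over time, or equal between MDTs, merely because few staff answered.

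The sentence also pulls against its own section, where a descriptive analysis with intervals leads to estimates and not to a verdict on a hypothesis.

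Section 8.1 says that the primary endpoint will inform a later amendment and expansion to further sites. A mistaken finding of no change could hide the improvement with experience that section 8.3 expects.

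**Working it through.** The protocol gives no SUS sample-size or power figure, so there is nothing to reproduce. The check asks how often a real change would come out non-significant.

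**Inputs from the protocol**
- About 20 staff at each of the two active MDTs (section 1), so 20 for one MDT or 20 + 20 = 40 pooled.
- 95% intervals (section 8.5), taken to imply a two-sided 5% test.

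**Assumptions (not in the protocol)**
- SUS SD of 15 or 20 points and within-person correlation 0.5.
- SD of change = SD × √(2(1 − 0.5)) = SD, so 15 or 20 points.
- True changes of 5 and 10 points.
- Two SUS scores per person and full response.

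**95% interval half-width for the mean change** = t × SD of change / √n
- n = 20, t(19) = 2.093: 2.093 × 15/√20 = 7.0 and 2.093 × 20/√20 = 9.4 points.
- n = 40, t(39) = 2.023: 2.023 × 15/√40 = 4.8 and 2.023 × 20/√40 = 6.4 points.

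**Chance of a non-significant result** = 1 − power of the paired t-test, from the noncentral t distribution with noncentrality = change / (SD of change / √n)

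| n | SD of change | True change | Noncentrality | Power | Missed |
|---|---|---|---|---|---|
| 20 | 15 | 5 | 1.49 | 29% | 71% |
| 20 | 20 | 5 | 1.12 | 19% | 81% |
| 20 | 15 | 10 | 2.98 | 81% | 19% |
| 20 | 20 | 10 | 2.24 | 56% | 44% |
| 40 | 15 | 5 | 2.11 | 54% | 46% |
| 40 | 20 | 5 | 1.58 | 34% | 66% |
| 40 | 15 | 10 | 4.22 | 98% | 2% |
| 40 | 20 | 10 | 3.16 | 87% | 13% |

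**Wider assumptions.** With SD 12 to 20 and correlation 0.3 to 0.7, power at n = 20 runs from 14% to 63% for 5 points and from 43% to over 99% for 10 points. The half-width runs from 4.4 to 11.1 points. At n = 40, power is 26-91% for 5 points and 74% to over 99% for 10.

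**Two MDTs of 20 compared with each other.** Half-width = t(38) × SD × √(2/20). With t = 2.024 this gives 9.6 points at SD 15 and 12.8 at SD 20.

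**What a claim of no difference would need.** For 80% power in a paired equivalence test at a true difference of zero, n = (SD of change × (1.645 + 1.282) / margin)². With SD of change 15, an assumed 5-point margin needs (15 × 2.927/5)² = 77.1, so 78 pairs. A 10-point margin needs 19.3, so 20 pairs. Whether the active MDTs could support such a claim therefore depends on a margin that the protocol does not give.

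**The case against.** The sentence is visibly missing words and may be a slip for testing a null hypothesis. No alpha or decision rule goes with it, so it should not be read as a settled rule. That is fair, but the wording still needs correcting, because what it names as the output is not a valid conclusion.

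A reader might infer that a real change in SUS would usually be reported as no difference. The documents do not support that. They give no effect size, and section 8.5 does not say that SUS is analysed separately by MDT. A mixed model could pool the teams. In the table, a 10-point change is detected more often than not in every row, and so is a 5-point change with 40 users and an SD of change of 15. The breast cancer MDT would add about 50 staff if it resumes.

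A reader might also take the pilot's disclaimers to cover SUS. They do not: section 8.6 says "While this pilot study is not powered to comprehensively evaluate secondary outcomes", and section 8.3 refers to health outcomes. Nor is any go/no-go rule tied to a SUS comparison. The protocol says only that the endpoint will inform later expansion.

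The planned 95% intervals would expose imprecision, which is a real safeguard but a partial one. Section 8.5 attaches them to means and proportions, gives skewed data an interquartile range, and specifies no interval for a change or a between-MDT contrast.

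Finally, stating a null and a margin is commonly left to the analysis plan. Their absence alone is not the complaint. The complaint is that the protocol already commits to accepting a null, and an analysis plan that followed it would inherit the error.

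One objection stands in full. Because only the onboarding assessment names SUS, the protocol does not specify a second score from which a change could be calculated.

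**Conclusion.** The point holds as a flaw in the stated inferential aim. Section 8.5 should not present acceptance of a null as the purpose of the SUS models. It gives no basis for doing so and contradicts its own descriptive approach.

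The practical size is conditional. With one active MDT and an SD of change of 15 to 20 points, 5-point changes would mostly be missed, while 10-point changes would be missed in a minority of cases. Pooling both active MDTs reduces both risks. These figures assume two scores per person and full response, and fewer responses would make them worse.

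The correction is worth making because it changes what may be concluded about a primary-endpoint instrument, and it costs almost nothing.

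**What to change.** 1. Delete the closing phrase of section 8.5 about accepting a null, and complete the sentence so that it says what the models estimate.
2. Report mean SUS with a 95% confidence interval at each administration.
3. Report any contrast as an estimate with a 95% confidence interval, whether within participants or between MDTs. Within-participant linkage is already provided for in section 16.6: "All participants will be assigned a non-identifiable study number and the data collected in the study will be linked to this number".
4. State that a non-significant result will not be read as no difference.
5. Reconcile section 8.3, which recommends repeated observation, with sections 11.2 to 11.4, and name the SUS administrations to be compared. If SUS is given only once, report its level with an interval and make no claim of change.

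The cost is a few lines in section 8.5, a small clarification of the survey schedule and the loss of a test verdict. If the sponsor chose to repeat SUS, it would add a ten-statement questionnaire to a survey that staff already receive.

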8.6 Expected Outcomes

The implementation of the Salutare One Referral Software is anticipated to enhance operational efficiencies by improving the quality of pre-assessment information and reducing the time spent preparing for meetings. These enhancements are expected to result in a higher percentage of patients receiving definitive MDT decisions, thereby shortening the patient pathway, including the pre-operative phase for surgical cases. Primary outcomes of the study will evaluate the increased confidence and satisfaction among MDT members in making complex clinical decisions. While this pilot study is not powered to comprehensively evaluate secondary outcomes, future study extension will be conducted to systematically assess the software's effectiveness in supporting MDT meetings and its impact on both patient outcomes and the experiences of MDT members.

